6.3.2 Vital Signs

Vital sign measurements (seated blood pressure, pulse rate, respiration rate, and temperature) at Visits 1, 3, 4, and 5 will be summarized using descriptive statistics (n, mean, standard deviation, median, minimum, maximum, and 95% CI). Similarly, change from Visit 1 at each visit will be summarized using descriptive statistics. For the summary of change statistics, the Baseline mean and standard deviation will be provided for the subset of subjects with available data for the change summary.

Values considered clinically significant by the investigator are to be flagged. Criteria for possibly significant post-baseline changes are presented in Table 3. Number and percentages of subjects with post-baseline values of clinical significance will be summarized by visit.

In addition, vital signs data will be listed for all subjects, inclusive of flags for whether the value is clinically significant in the investigator's judgment and whether it meets prespecified criteria as being possibly clinically significant post-basesline.

Vital sign values are considered as Possibly Clinically Significant (PCS) if they meet both the observed value criteria and the change from baseline criteria listed in Table 3 below.

Table 3: Possibly Clinically Significant Vital Sign Criteria

Vital Sign	Flag	PCS Criteria			
Parameter	rug	Observed Value	Change from Baseline		
Systolic	High (CH)	≥ 180 mmHg	Increase of ≥ 20 mmHg		
Blood Pressure (mmHg)	Low (CL)	≤90 mmHg	Decrease of ≥ 20 mmHg		
Diastolic	High (CH)	≥ 105 mmHg	Increase of ≥ 15 mmHg		
Blood Pressure (mmHg)	Low (CL)	≤ 50 mmHg	Decrease of ≥ 15 mmHg		
Pulse Rate (bpm)	High (CH)	≥ 120 bpm	Increase of ≥ 15 bpm		
	Low (CL)	≤ 50 bpm	Decrease of ≥ 15 bpm		

Note: A post-baseline value is considered a PCS value if it meets both criteria for observed value and change from

Note: PCS = potentially clinically significant.

CH = high PCS based on criterion value and percent increase from baseline.
CL = low PCS based on criterion value and percent decrease from baseline

The number and percentage of subjects with a PCS post-baseline vital sign value over all visits will be tabulated. Subjects with baseline and at least one post-baseline assessment will be included in the denominator and subjects who meet the PCS criteria at least once (based on all post-baseline assessments including unscheduled visits) will be included in the numerator. Subjects with a PCS post-baseline value will be flagged in the vital sign listing.

6.3.3 Clinical Laboratory Tests

The following tests will be performed at Screening (Week -2), Visit 5 (Week 26), and the Premature Termination visit (if applicable):

- Hematology:
 - RBC, including RBC count and hemoglobin
 - Total WBC count
 - Differential WBC count
 - Platelet count
- Serum chemistry: 0
 - Sodium
 - Potassium
 - Chloride
 - BUN
 - Creatinine

Clinical laboratory testing (hematology and chemistry) results at Visit 1 relative to Visit 5 (Week 26) based on Conventional Units will be summarized using descriptive statistics (n, mean, standard deviation, minimum, median, maximum, and 95% CI). Change from Visit 1 to Visit 5 will also be summarized. For the summary of change statistics, the Baseline mean and standard deviation will be provided for the subset of subjects with available data for the change summary.

Values outside the laboratory normal range are to be flagged as L (low) and H (high). Shift tables displaying the shift from laboratory normal range between Visit 1 and Visit 5 will be

generated. Criteria for possibly significant changes for selected parameters appear in Tables 4 and 5. The numbers and percentages of subjects meeting these criteria will be summarized by visit.

Table 4: Possibly Clinically Significant Hematology Values

Parameter	PCS values				
1 11 11 11 11 11	S.I. Units	Conventional Units			
White blood cells (WBC)	≤ 2.8 or ≥ 16 × 10°/L	$\leq 2.8 \text{ or } \geq 16 \times 10^9 / \text{L}$			
Lymphocytes	$\leq 0.5 \text{ or } \geq 4.5 \times 10^9/L$	$\leq 0.5 \text{ or } \geq 4.5 \times 10^9/L$			
Monocytes	$\geq 1.5 \times 10^9 / L$	≥ 1.5 × 10 ⁹ /L			
Neutrophils	$\leq 1.0 \times 10^9 / L$	$\leq 1.0 \times 10^9 / L$			
Eosinophils	$\geq 0.7 \times 10^9 / L$	$\geq 0.7 \times 10^9/L$			
Basophils	$\geq 0.4 \times 10^9 / L$	≥ 0.4 × 10 °/L			
Red blood cells (RBC)	M: $\leq 2.5 \times 10^{17}/L$ F: $\leq 2.0 \times 10^{12}/L$	M: ≤2.5×10°/mm³ F: ≤2.0×10°/mm³			
Hemoglobin	M: ≤115 g/L F: ≤95 g/L	M: ≤ 11.5 g/dL F: ≤ 9.5 g/dL			
Hematocrit	M: ≤ 0.37 F: ≤ 0.32	M: ≤ 37% F: ≤ 32%			
Platelet count	$\leq 75 \text{ or } \geq 700 \times 10^9 / \text{L}$	$\leq 75 \text{ or } \geq 700 \times 10^9/L$			

S.I. = International System of Units

Table 5: Possibly Clinically Significant Serum Chemistry Values

Parameter	PCS values				
	S.I. Units	Conventional Units			
Sodium	≤ 115 or ≥ 155 mmol/L	≤ 115 or ≥ 155 mEq/L			
Potassium	≤ 3.0 or ≥ 5.8 mmol/L	\leq 3.0 or \geq 5.8 mEg/L			
Glucose (random)	≤ 2.775 or ≥ 9.99 mmol/L	≤ 50 or ≥ 180 mg/dL			
BUN	≥ 30 mg/dL	> 30 mg/dL			
Creatinine	≥ 176.8 µmol/L	≥ 2.0 mg/dL			
Calcium, plasma	≤ 1.75 or ≥ 3.875 mmol/L	≤ 7 or ≥ 15.5 mg/dL			
ALT / SGPT	≥ 3 × ULN	≥ 3 × ULN			
AST / SGOT	≥ 3 × ULN	≥ 3 × ULN			
Alkaline phosphatase (ALK-P)	≥ 3 ×ULN	≥ 3 × ULN			
Total bilirubin	≥ 34.2 µmol/L	≥ 2.0 mg/dL			
Total protein	≤ 45 or ≥ 90 g/L	≤ 4.5 or ≥ 9.0 g/dL			
Albumin	≤ 25 or ≥ 65 g/L	$\leq 2.5 \text{ or } \geq 6.5 \text{ g/dL}$			
Creatinine clearance	< 70 mL/min	< 70 mL/min			

S.I. = International System of Units; ULN = upper limit of the [normal] reference range Medium = serum, unless otherwise noted

The number and percentage of subjects with a PCS post-baseline laboratory value over all visits will be tabulated. Subjects with baseline and at least one post-baseline assessment will be included in the denominator and subjects who meet the PCS criteria at least once (based on all post-baseline assessments including unscheduled visits) will be included in the numerator. Subjects with a PCS post-baseline value will be flagged in laboratory listings.

Clinical laboratory results will be listed for all subjects, inclusive of flags for whether or not the value is outside the laboratory normal range, considered significant by the investigator, or met the pre-specified criteria for being possibly clinically significant.

6.3.4 **12-Lead ECG**

ECGs will be assessed at visit 1 (screening), visit 3 (week 4), visit 4 (week 12), and visit 5 (week 26). ECG measurements will be collected in triplicate 2 minues apart and read at the investigator site. The following intervals will be collected: HR, PR, RR, QRS, QT, and QTc. The QTc interval will be presented by both the Bazett (QTcB = QT/(RR)^{1/2}) and the Fridericia (QTcF = QT/(RR)^{1/2}) corrections. For QTcF and QTcB at each study visit, the distribution of

maximum values (≤ 450 , $>450 - \le 480$, >450 males, >470 females, $>480 - \le 500$, and >

500 msec) as well as the distribution of the greatest change from visit 1 (0 or less [no increase], 1-29 msec, 30-60 msec, > 60 msec, and > 60 msec increase or > 500 msec) will be presented. Appropriate visit windows for categorizing results will be established prior to database lock and unblinding. When more than one value is available within a given visit window, the latest value will be used for tabulation purposes.

For the purposes of summary and analysis, results from the triplicate measurements at each visit will be averaged. ECG results will be summarized by visit using counts and percentages for abnormalities noted by the investigator and T-wave abnormalities, and using descriptive statistics (n, mean, standard deviation, minimum, median, maximum, and 95% CI) for interval data. For abnormality designations collected in triplicate, the worst outcome will be selected in the following order: Abnormal, Clinically Significant>Abnormal, Clinically Non-Significant>Normal. Any ECG abnormalities, based on clinical interpretation, will be reviewed for any emergent abnormalities that could be attributed to the new dosage form. Continuous ECG parameters will be summarized as change from Baseline (visit 1). For the summary of change statistics, the Baseline mean and standard deviation will be provided for the subset of subjects with available data for the change summary.

ECG results, including clinical interpretation and a flag for whether or not the value meets criteria for being possibly clinically significant, will be listed for all subjects.

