#### 12.3.3.3. Clinical Laboratory Tests

Clinical laboratory testing (hematology and chemistry) results at Visit 1 relative to Visit 5 (Week 26) will be summarized using descriptive statistics (n, mean, standard deviation, minimum, median, and maximum). Change from Visit 1 to Visit 5 will also be summarized.

Values outside the laboratory normal range as well as those considered clinically significant by the investigator are to be flagged as L (low) and H (high). Shift tables displaying the shift from laboratory normal range between Visit 1 and Visit 5 will be generated. Criteria for possibly significant changes will be established a priori for selected parameters. The numbers and percentages of subjects meeting these criteria will be summarized.

Clinical laboratory results will be listed for all subjects, inclusive of flags for whether or not the value is outside laboratory normal range, considered significant by the investigator, or meet the pre-specified criteria for being possibly clinically significant.

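### The laboratory PCS tables count subjects already beyond a limit at Visit 1 together with new cases, and no planned table fully separates the two

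*SAP*

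**What the plan says.** SAP 6.3.3 (Clinical Laboratory Tests) sets the denominator as follows: "Subjects with baseline and at least one post-baseline assessment will be included in the denominator". For the numerator, "subjects who meet the PCS criteria at least once (based on all post-baseline assessments including unscheduled visits) will be included in the numerator". Neither sentence refers to whether the baseline value was itself beyond the limit.

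The limits are in SAP Tables 4 (hematology) and 5 (serum chemistry). Both list observed-value limits only, for example creatinine at or above 2.0 mg/dL, and neither has a change-from-baseline column. Yet the SAP introduces them with "Criteria for possibly significant changes for selected parameters appear in Tables 4" and 5, and Protocol 12.3.3.3 says "Criteria for possibly significant changes will be established a priori for selected parameters".

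SAP 6.3.2 uses the same counting sentences for vital signs but defines the event differently: "Vital sign values are considered as Possibly Clinically Significant (PCS) if they meet both the observed value criteria and the change from baseline criteria".

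The planned outputs are Tables 14.3.4.2.3 and 14.3.4.3.3, which count subjects with a post-baseline PCS result by visit and overall. The SAP's list of planned outputs contains no new-onset version. The other laboratory displays are summaries of change from Visit 1 to Visit 5, "Shift tables displaying the shift from laboratory normal range between Visit 1 and Visit 5", and by-subject listings with flags.

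**The concern.** The trial is open-label and has no control arm, so nothing external shows how common a PCS value would be without study drug. Each subject's own Visit 1 value is the available reference, and the PCS count does not use it. The resulting percentage adds prevalence at entry to new occurrence, and a reader of the table cannot tell how much of it is which.

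Subjects beyond a limit at Visit 1 can be expected to be possible: the visible eligibility criteria (Protocol 8.2 and 8.3, partly redacted) contain no laboratory limit. Elsewhere the plan does take baseline into account. Vital-sign PCS requires a change. The adverse event definition in Protocol 12.3.3.1 covers new or worsened conditions and has those that pre-date Visit 1 summarized separately. ECG intervals are summarized as change from Visit 1.

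**Working it through.** The documents state no figure on this point, so there is nothing to reproduce. The check applies the rules to test cases and then shows how the rate behaves under assumed inputs.

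**1. Test cases (values chosen for illustration)**

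| Subject | Rule | Counted? |
|---|---|---|
| Creatinine 2.1 mg/dL at Visit 1, 2.1 after | SAP Table 5: 2.0 or more | Yes, with zero change |
| Systolic pressure 182 mmHg, then 184 | SAP Table 3: 180 or more and a rise of 20 or more | No, the rise is 2 |
| Systolic pressure 182 mmHg, then 204 | Same | Yes, the rise is 22 |

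The third row shows that the vital-sign rule does not drop subjects who start beyond the limit. It drops those who have not moved by the stated amount.

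**2. What the shift tables can show**

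- A subject with creatinine unchanged at 2.1 mg/dL falls in High-to-High, provided 2.1 is above the laboratory's normal range.
- A subject who starts above the normal range but below 2.0 mg/dL and then passes 2.0 also falls in High-to-High, although this is a new PCS case.
- A subject who is normal at Visits 1 and 5 with one PCS value at an unscheduled visit falls in Normal-to-Normal, yet is in the PCS numerator.

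So the shift tables separate subjects already out of range from those newly out of range, but they do not separate baseline PCS from new PCS.

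**3. Effect on the rate**

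Let b be the share of subjects PCS at Visit 1, s the share of those still PCS afterwards, and i the new-onset rate among the rest. None of these is given in the documents.

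- Rate as tabulated = b × s + (1 − b) × i
- New-onset rate = (1 − b) × i / (1 − b) = i

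With i = 1% and s = 60% to 80%:

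| b | s = 60% | s = 80% |
|---|---|---|
| 0% | 1.0% | 1.0% |
| 1% | 0.60 + 0.99 = 1.59% | 0.80 + 0.99 = 1.79% |
| 5% | 3.00 + 0.95 = 3.95% | 4.00 + 0.95 = 4.95% |
| 10% | 6.00 + 0.90 = 6.90% | 8.00 + 0.90 = 8.90% |

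**4. Second set of assumptions, as counts**

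Take N = 250 (the 26-week completion target), i = 2% and s = 50% to 90%.

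| b | Count as tabulated | Rate | Share already PCS at Visit 1 | New onset among those not PCS at Visit 1 |
|---|---|---|---|---|
| 0% | 5.0/250 | 2.0% | 0% | 5.0/250 = 2.0% |
| 2% | 7.4 to 9.4/250 | 3.0–3.8% | 34–48% | 4.9/245 = 2.0% |
| 10% | 17.0 to 27.0/250 | 6.8–10.8% | 74–83% | 4.5/225 = 2.0% |

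The direction follows from the rule. The size depends entirely on b, s and i.

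**The case against.** The strongest reply has four parts.

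*The label is accurate.* The outputs are titled as post-baseline PCS results. The SAP does not call them treatment-emergent or attribute them to drug, the analyses are descriptive, and no decision rule uses the percentage. This stands. A reader might infer that the SAP presents pre-existing abnormalities as drug effects; the text does not say so. What remains is that the table mixes two kinds of case.

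*Other displays help.* Change summaries, shift tables, and listings with PCS, normal-range and investigator flags are all planned, and abnormal laboratory findings can be adverse events under Protocol 11.3.1. A reader might take the PCS percentage to be the main laboratory safety result, but nothing in the documents ranks it first. The separation is only partial, however, and recovering PCS status at Visit 1 would mean going through listings subject by subject.

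*The effect may be small.* Several limits are far out, such as sodium at or below 115 or at or above 155 mmol/L and platelets at or below 75 or at or above 700 × 10⁹/L. Many Table 5 analytes, including glucose, ALT, AST and bilirubin, are not among the scheduled tests listed in 6.3.3. At 1% baseline prevalence the first illustration adds only 0.6 to 0.8 percentage points. All of this is fair, and it limits the claim.

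*Dropping baseline-PCS subjects would lose safety information.* Creatinine rising from 2.1 to 4.0 mg/dL would leave the count. For subjects rolling over from CLR_09_21, Visit 1 may coincide with that trial's final visit (Protocol Table 1, footnote a), so a Visit 1 abnormality may have arisen on earlier treatment. This stands in full. A reader might infer that the existing count should be replaced; the documents do not support that, and the vital-sign rule itself keeps baseline-PCS subjects who change enough.

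**Conclusion.** The point holds as a modest, inexpensive improvement to the tabulation. As written, the laboratory PCS count ignores baseline status, does not match the plan's own description of the limits as criteria for changes, and differs from the vital-sign rule. No planned table fully separates new from pre-existing PCS values.

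The size cannot be derived from the documents. The effect is nil for any parameter with no PCS values at Visit 1. With 1% new onset and 60–80% persistence, both assumed, the tabulated rate is 1.6–1.8% at 1% baseline prevalence, 4.0–5.0% at 5% and 6.9–8.9% at 10%. A reader might conclude from the upper end that the table will overstate new abnormalities several-fold. That would need a baseline prevalence of around 5–10%, which the documents do not show for any parameter.

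Nor is every Visit 1 abnormality mere background: in roll-over subjects it may itself be a treatment finding, so it has to stay visible.

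**What to change.** Keep the existing count in Tables 14.3.4.2.3 and 14.3.4.3.3 and add the following, overall and by Safety Group:

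1. **New-onset PCS**, per parameter and direction (low or high). The numerator is subjects not PCS in that direction at Visit 1 with at least one post-baseline PCS value in that direction, unscheduled visits included. The denominator is subjects not PCS in that direction at Visit 1 with at least one post-baseline value.
2. **Subjects already PCS at Visit 1**, as a separate line or as a cross-tabulation of baseline PCS status against worst post-baseline PCS status. It should show whether they worsened, with the definition of worsening written into the SAP before database lock.

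Add a footnote that, for roll-over subjects, Visit 1 may coincide with the final CLR_09_21 visit, so an abnormality at Visit 1 may have arisen on earlier treatment.

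The cost is a few sentences in SAP 6.3.3, slightly longer tables and a small programming addition. All the data are already collected.

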#### 11.4.4. 12-Lead ECG

ECG will be performed at Visit 1 (Week -2), Visit 3 (Week 4), Visit 4 (Week 12), Visit 5 (Week 26), and during the premature termination visit (if applicable).

ECG measurements will be collected in triplicate 2 minutes apart and read at the site. The following intervals will be collected: PR interval, QRS, and ventricular rate; the presence of T-waves will be noted.

A clinically significant change in any post-dosing ECG will be reported as an AE.

Confidential Page 33 of 47

[figure not shown]

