#### 12.3.3.4. 12-Lead ECG

[figure not shown]
Any ECG abnormalities, based on clinical interpretation, will be listed and reviewed for any emergent abnormalities that could be attributed to the new dosage form. Proportion of subjects with change from baseline will be summarized.

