2. INTRODUCTION

This Statistical Analysis Plan (SAP) describes the planned statistical analyses to be performed for the analysis of data from Study CLR_11_04, "A Clinical Evaluation of the Safety of When Administered Once Daily to Subjects with Spasticity due to Multiple Sclerosis (MS): An Open Label, Long Term, Safety Trial."

The SAP is prepared to provide a more technical and detailed elaboration of the principal statistical features stated in the protocol. The SAP will ensure that the tables, listings, and figures that will be produced and statistical methods that will be used are complete and accurate and will allow valid conclusions to be drawn. In the development of this SAP, the following documents were used:

- Protocol Number Version 1.0 Amendent 02, 17 Dec 2015
- Electronic Case Report Form (eCRF), 24 Jun 2013

The principles in the following guidance documents are followed in preparation of this SAP:

- International Conference on Harmonisation (ICH) E3 (1995): Structure and Content of Clinical Study Reports
- ICH E6 (1996): Guideline for Good Clinical Practice
- ICH E9 (1998): Statistical Principles for Clinical Trials

In the event that a discrepancy is found between the descriptions in the statistical section of the protocol and this document, the description in this document supersedes the descriptions in the statistical section of the protocol.

The Biostatistician is responsible for updating the SAP throughout the life of the study as needed. The responsible party at SPARC Ltd. will be required to review and approve all versions of the SAP.

Version 1.0

30Oct2017

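### Protocol 11.4.4 and SAP 6.3.4 list different ECG intervals, and only the SAP list includes the QT that its QTc tables need; the Fridericia exponent should also be checked in the source PDF

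*SAP*

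**What the plan says.** Protocol 11.4.4, in the procedures part of the Protocol, has ECGs taken in triplicate, two minutes apart, and read at the site. On what is recorded it says: "The following intervals will be collected: PR interval, QRS, and ventricular rate; the presence of T-waves will be noted".

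SAP 6.3.4 describes the same triplicate, site-read ECGs but gives a longer list: "The following intervals will be collected: HR, PR, RR, QRS, QT, and QTc". It then presents QTc by "both the Bazett (QTcB = QT/(RR)^{1/2}) and the Fridericia (QTcF = QT/(RR)^{1/2}) corrections". For QTcF and QTcB at each visit it plans a distribution of maximum values, with cut-offs that include 450, 480 and 500 msec, and "the distribution of the greatest change from visit 1 (0 or less [no increase], 1-29 msec, 30-60 msec", followed by bands above 60 msec.

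The visible text of Protocol 12.3.3.4 does not mention QT. It says only: "Proportion of subjects with change from baseline will be summarized".

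Where the two documents differ, SAP section 2 states that "the description in this document supersedes the descriptions in the statistical section of the protocol". The same section names the "Electronic Case Report Form (eCRF), 24 Jun 2013" among the documents used to write the SAP.

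**The concern.** Every QTcB and QTcF table in SAP 6.3.4 needs a QT measurement. A site working from Protocol 11.4.4 alone would have no instruction to record one, and the documents describe no central reading that would supply it. If the case report form followed the Protocol list, the QTc tables would have no input.

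The second worry is the formula. The SAP names two corrections and plans separate results for each, yet as read it gives both the same exponent. Fridericia is the cube-root correction, and no cube root appears anywhere in either document. Programmed as read, the two sets of results would be identical, and those labelled Fridericia would hold Bazett values.

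ECG results are a named safety endpoint in Protocol 7.2 and SAP 4.1. This is an open-label safety trial whose output is descriptive, so errors of this kind would fall on that output. No hypothesis test or sample size depends on QTc.

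**Working it through.** **The two lists side by side**

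| Quantity | Protocol 11.4.4 | SAP 6.3.4 | Obtainable from the Protocol list? |
|---|---|---|---|
| PR | yes | yes | yes |
| QRS | yes | yes | yes |
| Heart (ventricular) rate | yes | yes | yes |
| RR | no | yes | yes: RR = 60/rate, in seconds |
| QT | no | yes | no |
| QTc | no | yes | no: needs QT |

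The Protocol also notes T-waves, but their presence does not time the end of the T-wave. QT therefore cannot be reconstructed from PR, QRS and rate.

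**Does the precedence rule settle it?** No. It covers the Protocol's statistical section, which is section 12. The list of recorded intervals is in section 11. The SAP can override how ECG data are analysed under Protocol 12.3.3.4, but not what sites are told to record under 11.4.4.

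**Is the exponent readable?** Not reliably. In SAP Table 4 the red-cell limits in SI units read "M: $\leq 2.5 \times 10^{17}/L$ F: $\leq 2.0 \times 10^{12}/L": the male power of ten is 17 beside 12 for females. In the same table the white-cell limit shows a degree sign where the adjacent column shows a 9. The red-cell limit per cubic millimetre also shows a degree sign. There the power should be 6, because one litre is 10^6 mm³ and the female limit is 2.0 × 10^12 per litre. So two different superscripts, 9 and 6, have come out as the same symbol. A 1/3 that came out as 1/2 would be a failure of the same kind.

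**Size if the source does show 1/2.** The formula as read gives QTcB − QTcF = 0 at every heart rate. Its ratio to the cube-root form is

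[QT/RR^(1/2)] / [QT/RR^(1/3)] = RR^(1/3 − 1/2) = RR^(−1/6), with RR = 60/rate.

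- 50 bpm: RR = 1.2, ratio 0.970 (3.0% low)
- 60 bpm: RR = 1.0, ratio 1.000
- 80 bpm: RR = 0.75, ratio 1.049 (4.9% high)
- 100 bpm: RR = 0.6, ratio 1.089 (8.9% high)

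These rates are assumptions; the documents give none. One assumed value in each direction shows that categories can move. A cube-root QTcF of 450 msec at 80 bpm would be tabulated as 450 × 1.0491 = 472.1, in the band above 450. One of 460 msec at 50 bpm would be tabulated as 460 × 0.9701 = 446.2, in the band at or below 450. The ratio depends on rate, so change from Visit 1 is distorted as well whenever the rate differs between visits.

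**The case against.** The strongest reply on the lists is that the SAP says outright that QT and QTc are collected, and that it was written with the eCRF to hand. SAP Appendix 2 plans a listing of continuous ECG data. The Protocol sentence does not say that only those intervals are recorded, and figures are missing from the text of both Protocol 11.4.4 and 12.3.3.4. The two documents may also reflect different versions: SAP 3.2 admits subjects from outside CLR_09_21, whereas Protocol inclusion criterion 6 requires completion of that trial's Part 3. All of this stands. A reader might infer that QT was never recorded, and the documents do not support that. They do support a contradiction between two lists that should agree.

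On the formula, a reader might infer that the SAP specifies Fridericia wrongly. That is not supported either, since the damaged superscripts make a misreading of one digit quite possible. Naming Fridericia separately also makes the intent plain, and two identical sets of results would be conspicuous. SAP section 7 provides for independent checking, which might catch the slip. That is only a partial safeguard, because one of its tests is agreement with the methods described in the SAP, and a wrong formula coded faithfully would pass it.

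A reader might also ask whether QTcB and QTcF are calculated or taken from the site reading. SAP 6.3.4 writes both as functions of QT and RR, so calculation is the natural reading.

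**Conclusion.** The contradiction between Protocol 11.4.4 and SAP 6.3.4 is established by two complete sentences and rests on no superscript. QT, the one input that all the QTc tables require, is in the SAP list and cannot be recovered from the Protocol list. Whether sites recorded it is unknown without the eCRF.

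The exponent is a query, not a demonstrated error. If the source shows 1/3, no formula change is needed. If it shows 1/2, the stated QTcF is Bazett's value, off by roughly −3% to +9% between 50 and 100 bpm, and subjects could be placed in the wrong descriptive QTcF category in either direction. The documents do not allow an estimate of how many.

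Both matters affect descriptive ECG safety tables only. They are worth correcting because QTc results are planned output of a safety trial and the correction is small.

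**What to change.** 1. Add QT to Protocol 11.4.4, together with RR or a statement that RR = 60/rate, so that the list matches SAP 6.3.4 and the eCRF of 24 Jun 2013. If that eCRF did not capture QT, state in the SAP that QTc cannot be analysed.

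2. Check the exponent in the source PDF of SAP 6.3.4. If it shows 1/2, replace the Fridericia formula with QTcF = QT/(RR)^(1/3), with RR in seconds. If it shows 1/3, leave the formula as it is.

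The cost is one look at the eCRF, one look at the source PDF, a line in the Protocol and at most one exponent and a unit in the SAP. If QT was not captured, the cost is a sentence in the SAP and the loss of the QTc tables.

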# 10.5. Visit 5 (Day 182 $\pm$ 5 days/Week 26), or Premature Termination

- Physical and neurologic examinations will be performed during Visit 5, but will be performed as needed during the Premature Termination visit to follow the resolution of any adverse events
- A urine pregnancy test will be performed
- Vital Signs (sitting), after resting for 5 minutes, will be obtained
- Clinical laboratory testing will be performed including hematology (RBC count, hemoglobin, total and differential WBC count, platelet count), and serum chemistry including sodium, potassium, chloride, BUN, and creatinine
- A 12-lead ECG will be performed in triplicate. 12-lead ECG should be performed at the Premature Termination visit, as needed, in order to follow adverse events to resolution.
- C-SSRS assessment will be performed
- Concomitant medication and physical therapy will be recorded
- AEs will be recorded
- Study medication and Subject diary collected and reviewed from previous visit for compliance
- Study medication and subject diary will be dispensed
- The next trial visit will be scheduled.

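### SAP 6.3.4 sets out QTc outliers by visit and states no count of subjects who ever exceed 500 msec or a 60 msec rise, unlike vital signs and laboratory values

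*SAP*

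**What the plan says.** SAP 6.3.4 (12-Lead ECG) names the ECG time points: "ECGs will be assessed at visit 1 (screening), visit 3 (week 4), visit 4 (week 12), and visit 5 (week 26"). The outlier display is then defined by visit: "For QTcF and QTcB at each study visit, the distribution of" maximum values in bands running up to above 500 msec, and likewise the greatest change from Visit 1, in bands that include a rise above 60 msec and a composite of that rise or a value above 500 msec.

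Three rules decide which number enters a band:

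- Triplicates: "results from the triplicate measurements at each visit will be averaged".
- Windows: "Appropriate visit windows for categorizing results will be established prior to database lock and unblinding".
- Several values in one window: "When more than one value is available within a given visit window, the latest value will be used for tabulation purposes".

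For vital signs, SAP 6.3.2 adds a count over all visits, in which "subjects who meet the PCS criteria at least once (based on all post-baseline assessments including unscheduled visits) will be included in the numerator". SAP 6.3.3 has the same provision for laboratory values. In both, the denominator is subjects with a baseline and at least one post-baseline assessment. SAP 6.3.4 has no matching sentence.

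Protocol 10.5 provides for an ECG outside the regular schedule: "12-lead ECG should be performed at the Premature Termination visit, as needed, in order to follow adverse events to resolution". SAP 6.3.4 does not mention it, although the schedule table in SAP 3.2.3 places Premature Termination in the Visit 5 column.

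**The concern.** Safety is the only objective of this trial, so the number of subjects who at any time had marked QTc prolongation is a main descriptive result. Percentages by visit do not give it. The same subject may appear at several visits, or different subjects at each, and the table looks identical in both cases.

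The wording also pulls in two directions. Maximum and greatest suggest a worst-case summary. Once triplicates are averaged and one latest value is kept per window, each subject has a single value per visit, and there is little left to take a maximum of. Two programmers could build different tables from this text. The stricter reading, by visit with the latest value, can lose an outlier altogether.

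**Working it through.** The documents state no QTc outlier rate and no figure on this point, so there is nothing to reproduce. The check has three parts.

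**1. The three safety domains side by side**

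| Domain | SAP section | By-visit summary | Stated count over all visits | Unscheduled values | Planned outlier table |
|---|---|---|---|---|---|
| Vital signs | 6.3.2 | yes | yes | included | 14.3.4.1.2, by visit and overall |
| Laboratory | 6.3.3 | yes | yes | included | 14.3.4.2.3 and 14.3.4.3.3, by visit and overall |
| QTc | 6.3.4 | yes | none | not addressed | none separate; only the general ECG table, 14.3.4.4 |

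**2. What by-visit counts can tell**

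Let k1, k2 and k3 be the numbers of subjects in a category at the three post-baseline ECG visits (3, 4 and 5). For the values tabulated,

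max(k1, k2, k3) ≤ subjects ever in the category ≤ k1 + k2 + k3.

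The lower end applies if the same subjects recur, the upper end if no subject recurs. With equal counts the range spans a factor of 3.

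The per-visit rates below are assumptions. N = 350 is the enrolment in Protocol 12.1, taken here as subjects with all three ECGs.

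| Assumed rate per visit | Subjects per visit | Ever: lowest | Ever: highest |
|---|---|---|---|
| 0.5% | 350 × 0.005 = 1.75, about 2 | 2 | 3 × 2 = 6 |
| 1% | 350 × 0.01 = 3.5, about 4 | 4 | 3 × 4 = 12 |
| 2% | 350 × 0.02 = 7 | 7 (7/350 = 2.0%) | 3 × 7 = 21 (21/350 = 6.0%) |

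Independence between visits gives 1 − (1 − 0.02)³ = 5.88% at the 2% rate, or 20.6 subjects. That lies inside the range and is not its upper limit. With the SAP's enrolment of 550, the 2% rate gives 11 per visit and 11 to 33 ever. The factor of 3 does not depend on N.

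**3. What the latest-value rule can remove**

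Take assumed values for one subject: 440 msec at Visit 1, then 510 and later 470 msec in the same post-baseline window.

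- Tabulated: 470 msec, change 470 − 440 = +30 msec.
- Highest: 510 msec, change 510 − 440 = +70 msec.

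The subject is counted neither above 500 msec nor above a 60 msec rise. The bounds in part 2 cover only tabulated values, so such a subject would be missing from them as well.

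A Premature Termination ECG raises the same issue. The last scheduled ECG is at Week 26, while treatment is planned to a year or more. Depending on the windows chosen, a later termination ECG could be tabulated, displace the subject's Week 26 value, or fall in no window.

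**The case against.** A reader might infer that unscheduled and termination ECGs are dropped from the QTc counts. The documents do not say so. Results are assigned by window, the windows are still to be set, and termination shares the Visit 5 column. An off-schedule ECG inside a window is eligible and may even replace the scheduled one. Protocol 10.7 lists no ECG among the unscheduled-visit procedures, so how many such ECGs there will be is unknown. What stands is that these ECGs have no stated place in the counts.

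A reader might also infer that the any-time number goes wholly unreported. That too is more than the text supports. All ECG results are listed by subject (Listings 16.2.10.1 and 16.2.10.2), so the number could be counted by hand. Protocol 11.4.4 has clinically significant post-dosing ECG changes reported as adverse events. Protocol 12.3.3.4 plans a proportion of subjects with change from baseline, with no by-visit limit. None of these is a prespecified count at 500 or 60 msec. The listing's flag for possible clinical significance has no ECG criteria behind it, since SAP Tables 3 to 5 cover only vital signs and laboratory values.

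Two further points are fair. The title of Table 14.3.4.4 says neither by visit nor overall, and its shell is not in the documents, so an overall row cannot be ruled out. The words maximum and greatest may show that a worst-case summary was intended. Both argue for saying so in the text.

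Finally, the study is descriptive with no QTc hypothesis, and repeated QTc values within a subject are usually positively correlated, which makes the upper end of the range less likely. The plan also aims for only about 250 subjects completing 26 weeks, so fewer than 350 may have all three ECGs. This limits the weight of the illustration but does not supply the missing count.

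**Conclusion.** The point holds as a gap and an ambiguity in SAP 6.3.4. The section specifies QTc outliers by visit, uses the latest value per window, and states no count over all visits, although the SAP states one for vital signs and laboratory values. No planned table is stated to give the number of subjects who ever exceed 500 msec or a 60 msec rise.

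The conclusion rests on the absence of an any-time sentence in 6.3.4 and on the table list. It does not rest on a claim that any ECG is excluded, which cannot be decided until the windows are set. The size is uncertainty in the any-time count by up to a factor of 3: 7 to 21 of 350 subjects under the assumed 2% per visit with complete ECGs. Any outlier displaced by a later value or lying outside every window would come on top. The rates show the arithmetic and do not predict what this trial will find. The change should be made because it is nearly free and applies the SAP's own rule to data already collected.

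**What to change.** Add to SAP 6.3.4, and to Table 14.3.4.4, an any-post-baseline summary along these lines:

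*For each subject, the highest QTcF and QTcB and the largest increase from Visit 1 will be taken over all post-baseline ECGs, including unscheduled and Premature Termination ECGs, without applying the latest-value rule. The numbers and percentages in each category will be based on subjects with a Visit 1 ECG and at least one later ECG.*

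Triplicate averaging can stay as it is. The same edit should say whether maximum and greatest change refer to this summary or to the by-visit rows, and should state the ECG windows, including where a termination ECG after Week 26 belongs.

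The any-post-baseline summary costs one SAP sentence and one extra row per table. It needs no new data and changes no study procedure.
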